## 9.2 Secondary Endpoints

### 9.2.1 Proportions

The same method used in the primary endpoint will be repeated for the following secondary efficacy endpoints:

- Proportion of subjects alive and free of respiratory failure at Day 60
- Proportion of subjects alive and discharged from ICU at Days 14 and 28
- All-cause mortality at Day 60 and Day 90

Subjects who discontinue the study prior to the study day end will be considered treatment failures.

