5.1. Subject Inclusion Criteria

Subjects are eligible to be included in the study only if all the following criteria apply:

1. Confirmed infection with SARS-CoV-2 per World Health Organization (WHO) criteria (including positive RT-PCR nucleic acid test of any specimen [eg, respiratory, blood, urine, stool, or other bodily fluid]) within 7 days of randomization. Positive RT-PCR test results more than 7 days prior to randomization is allowed if the site is unable to obtain a repeat sample and if the subject has progressive disease consistent with COVID-19.
2. COVID-19 pneumonia (documented radiographically) requiring hospitalization and oxygen saturation <94% on room air or subject requires supplemental oxygen.
3. Age ≥ 18 years at the time of signing the informed consent form
4. Subject or family member/caregiver must have provided written informed consent which includes signing the institutional review board approved consent form prior to participating in any study related activity. However, if obtaining written informed consent is not possible, other procedures as provided in the March 27th, 2020 FDA Guidance on Conduct of Clinical Trials of Medical Products during COVID-19 Pandemic, Question 10, may be used.
5. Able to swallow capsules
6. Willing to follow contraception guidelines

If a female, be sterile (surgically or biologically)* or at least one year post-menopausal**, or have a monogamous partner who is surgically sterile, or have a same sex partner, or if in a heterosexual relationship, must agree to do the following for at least 1 month after receiving IP:

- Practice abstinence
- Use at least 1 of the following medically acceptable methods of birth control:
 - Hormonal methods such as oral, implantable, injectable, vaginal ring, or transdermal contraceptives (must have started a minimum of 1 full cycle, based on the subject's usual menstrual cycle period, before IP dose)
 - Intrauterine device
 - Double-barrier method (condoms, sponge, or diaphragm with spermicidal jellies or cream).

**Defined as having had a hysterectomy and/or bilateral oophorectomy, bilateral salpingectomy or bilateral tubal ligation/occlusion at least 6 weeks prior to screening; or having a congenital or acquired condition that prevents childbearing*

***Defined as at least 12 months with no menses without an alternative medical cause)

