9.4.5. Secondary Endpoints (Efficacy)

The proportion of subjects alive and discharged from the ICU at Day 14 and Day 28 and the proportion alive and free of respiratory failure at Day 60 and will be presented and analyzed as described for the primary efficacy endpoint. Subjects who discontinue from the study prior to each study day will be considered treatment failures.

Clinical Status will be assessed using a generalized linear mixed model, assuming a multinomial distribution. The model will include the Day 1 value as a covariate with fixed effects of group,

study day and group-by-study day interaction and subject as a random effect. If the group-by-study day interaction is found to be statistically significant then comparisons between groups at Day 7, Day 14 and Day 28 will be obtained from this model. Additionally, stacked bar charts will be presented for the proportion of subjects in each category by group and study day.

For the time from randomization to first occurrence of respiratory failure or death on study due to any cause, the Kaplan-Meier method will be applied. Subjects will be censored at the time of last follow-up. For each group, the 25th percentile, median and 75th percentile will be presented, if possible. Possible differences between groups will be assessed by the log-rank test.

The total number of deaths per group will be presented for All-cause mortality at Day 90.

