## **6.0 ANALYSIS POPULATIONS**

### **6.1 Full Analysis Set (FAS)**

The full analysis set (FAS) includes all randomized patients. This is the intention to treat population. The FAS is based on the treatment allocated (as randomized). All efficacy endpoints will be analyzed using the FAS.

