### **7.2 Summary Statistics**

Analysis will be summarized by treatment group of STI-5656 plus SOC or Placebo plus SOC, unless specified otherwise.

- Continuous endpoints will be summarized using descriptive statistics (number of participants, mean, standard deviation [SD], median, and maximum values) for each cohort. The summary statistic n will be the number of subjects with non-missing values. All means and medians will be reported to one more significant digit than the values being analyzed. Standard errors and standard deviations will be reported to two more significant digits than the values being analyzed. The minimum and maximum will be reported to the same number of significant digits as the values being analyzed.
- Categorical endpoints will be summarized as the number and percentage of participants per category for each cohort. Percentages will be out of the number of subjects in the population being reported, unless otherwise noted. All percentages will be rounded to one decimal point. The number and percentage of subjects will always be presented in the form XX (XX.X%) where the percentage is in parentheses. To ensure completeness, all summaries for categorical and discrete variables will include all categories, even if none of the subjects had a response in a particular category. Denominators for each analysis will be based on the population of interest (e.g., safety population; subjects with non-missing data).
- Subject listings of data will be presented for all enrolled subjects unless specified otherwise.

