## **9.0 EFFICACY EVALUATION**

### **9.1 Primary Endpoint**

The primary efficacy endpoint is the proportion of subjects alive and free of respiratory failure at Day 28, where respiratory failure, is defined based on resource utilization of any of the following modalities:

- Noninvasive positive pressure ventilation or continuous positive airway pressure
- Endotracheal intubation and mechanical ventilation
- Oxygen delivered by high-flow nasal cannula (heated, humidified, oxygen delivered via reinforced nasal cannula at flow rates  $>20$  L/min with fraction of delivered oxygen  $\geq 0.5$ )
- Extracorporeal membrane oxygenation

The number and percentage of subjects will be presented by treatment group using FAS population. Primary analysis to evaluate the differences between groups will utilize a

generalized linear mixed model, assuming a binomial distribution and a logit link. The model will include group as a fixed effect. Subjects who discontinue the study prior to Day 28 will be considered treatment failures.

Sensitivity analyses may be performed using PP population.

After 40 subjects have been enrolled and completed Day 28, an interim futility analysis will be performed to examine the proportion of subjects alive and free of respiratory failure at Day 28. The interim analysis is a non-binding analysis. See Section 7.4 for details.

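### The endpoint of being alive and discharged from ICU is undefined for subjects never admitted to ICU, and read literally on all randomised subjects it can penalise preventing ICU admission

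*SAP*

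**What the plan says.** SAP 9.2.1 applies the primary-endpoint method to "Proportion of subjects alive and discharged from ICU at Days 14 and 28". Protocol 9.4.5 has the same endpoint, "The proportion of subjects alive and discharged from the ICU at Day 14 and Day 28", also analysed like the primary. That method is a logistic model with group as its only stated fixed effect, and for the primary endpoint SAP 9.1 states that "The number and percentage of subjects will be presented by treatment group using FAS population".

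The population is everyone randomised. SAP 6.1 states that "All efficacy endpoints will be analyzed using the FAS". SAP 7.2 sets the default denominator: "Percentages will be out of the number of subjects in the population being reported, unless otherwise noted". Nothing different is noted for the ICU endpoint.

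Entry is by hospitalisation and oxygen need, not ICU care. Protocol 5.1 asks for "COVID-19 pneumonia (documented radiographically) requiring hospitalization and oxygen saturation <94% on room air or subject requires supplemental oxygen". ICU care is neither required nor excluded.

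The only failure rule in SAP 9.2.1 concerns dropout: "Subjects who discontinue the study prior to the study day end will be considered treatment failures". Protocol 9.4.5 has an equivalent rule. Neither place mentions subjects who were never in an ICU.

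**The concern.** Discharge from an ICU presupposes admission to one. A subject who recovers on the ward has one of the best courses available in this trial, yet does not fit the endpoint as worded. A binary analysis of all randomised subjects must still give that subject a value. There are three candidates:

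- **Non-success**, the literal result. Preventing ICU admission then lowers the success rate.
- **Excluded**, with only ICU-admitted subjects analysed. This selects on an event after randomisation that treatment may influence, so the arms are no longer comparable by design, and any benefit through prevention is lost.
- **Success**, meaning alive and not in ICU on the day. This keeps the randomised comparison and points the right way, but neither document states it.

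The candidates can point in different directions on the same data. If the rule is not fixed before unblinding, it could be chosen with results in view. The primary endpoint does not have this problem: being alive and free of respiratory failure is a state that a subject who never deteriorated satisfies.

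**Working it through.** **The plan's own figure.** None is stated for this endpoint. The stated power (80% in SAP 5.0; 80.8% in SAP 7.4) concerns the primary endpoint. The continuity-corrected two-proportion formula for 95.7% vs 70% gives 40 per arm at 80% power, which agrees with the plan but has no bearing here.

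**Inputs.** From the documents: 40 per arm, all randomised subjects in the denominator, no ICU requirement at entry. Assumed, because the documents give no ICU rates:

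- *c* = share of an arm ever admitted to ICU: 20% vs 10%, 30% vs 15% and 50% vs 25% (placebo vs active). A fourth pair, 30% vs 4.3%, borrows the complements of the primary-endpoint rates (100 − 70 and 100 − 95.7). It is only an illustration, since respiratory failure is not the same as ICU admission.
- *s* = share of admitted subjects alive and discharged from ICU by the analysis day: 40% to 70%, equal in both arms.
- All never-ICU subjects are alive on the analysis day.

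**Formulas for one arm.**

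- Literal reading, never-ICU as non-success: *c* × *s*
- Alive and not in ICU: (1 − *c*) + *c* × *s*
- ICU-admitted subjects only: *s*

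**One case in full.** Admission 30% vs 15%, *s* = 0.5:

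- Literal: 0.30 × 0.5 = 15.0% placebo; 0.15 × 0.5 = 7.5% active. That is 6 vs 3 of 40, or −7.5 points for active.
- Alive and not in ICU: 0.70 + 0.15 = 85.0% placebo; 0.85 + 0.075 = 92.5% active. That is 34 vs 37 of 40, or +7.5 points.
- ICU-admitted only: 50% vs 50%, no difference.

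**Range** (all in %, placebo vs active; differences are active minus placebo, in points).

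| Admitted | *s* | Literal | Diff. | Alive, not in ICU | Diff. |
|---|---|---|---|---|---|
| 20 vs 10 | 40 | 8.0 vs 4.0 | −4.0 | 88.0 vs 94.0 | +6.0 |
| 20 vs 10 | 70 | 14.0 vs 7.0 | −7.0 | 94.0 vs 97.0 | +3.0 |
| 30 vs 15 | 40 | 12.0 vs 6.0 | −6.0 | 82.0 vs 91.0 | +9.0 |
| 30 vs 15 | 70 | 21.0 vs 10.5 | −10.5 | 91.0 vs 95.5 | +4.5 |
| 50 vs 25 | 40 | 20.0 vs 10.0 | −10.0 | 70.0 vs 85.0 | +15.0 |
| 50 vs 25 | 70 | 35.0 vs 17.5 | −17.5 | 85.0 vs 92.5 | +7.5 |
| 30 vs 4.3 | 40 | 12.0 vs 1.7 | −10.3 | 82.0 vs 97.4 | +15.4 |
| 30 vs 4.3 | 70 | 21.0 vs 3.0 | −18.0 | 91.0 vs 98.7 | +7.7 |

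**When the sign does not reverse.** The literal reading favours active only if *c* × *s* is larger on active. If active halves admission, its *s* must be more than double that of placebo: with 40% on placebo it must exceed 80%, and with 50% or more on placebo this is impossible. If nearly everyone is in ICU at baseline, *c* is close to 1 in both arms, both all-randomised readings reduce to *s*, and the problem disappears.

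**The case against.** A reader might infer that the plan counts never-ICU patients as failures, so that preventing ICU admission would look harmful. The documents do not support this. They are silent on such subjects, and the one failure rule concerns discontinuation. A programmer could reasonably code *alive and not in ICU*, which is a valid comparison of all randomised subjects in the right direction. It would therefore also be wrong to say that no available reading works.

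SAP 7.2 adds that "Denominators for each analysis will be based on the population of interest (e.g., safety population; subjects with non-missing data"), which leaves some room for a subset denominator. Entry does not exclude ICU care, and for subjects already in ICU at baseline the literal wording behaves properly. With no ICU rates in the documents, neither the occurrence nor the size of a reversal can be established.

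This is also one secondary endpoint among many. It does not feed the primary analysis, the sample size or the futility rule, and the endpoints on ICU days and days alive outside hospital would help expose a spurious harm. Finally, SAP 1.0 cites protocol version 5.0, while the protocol supplied is version 4.0, so a clarification in the later version cannot be ruled out.

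These points limit the claim but do not remove it. The stated wording on the stated population gives the literal reading, and SAP 7.2 names no ICU subset for this endpoint. SAP 1.0 says that the SAP supersedes the protocol's analysis description, and the SAP, written against version 5.0, contains no rule. Silence that allows codings with opposite directions needs to be resolved.

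**Conclusion.** The point holds as a gap in definition with a possible directional consequence. The endpoint has no rule for never-ICU subjects. Its literal reading on all randomised subjects can score an arm lower for preventing ICU admission, and restricting to admitted subjects would condition on a post-randomisation event.

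Over the assumed range, the literal reading gives −4 to −18 points for active and *alive and not in ICU* gives +3 to +15.4 points. These figures rest on assumed admission rates, equal outcome among those admitted, and survival of all never-ICU subjects. They show direction and rough scale and do not predict this trial's result.

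**What to change.** Before unblinding, redefine the endpoint as alive and not in ICU at Day 14 and at Day 28, on the full analysis set, with never-ICU survivors counted as successes. Keep the existing rule for subjects who discontinue. The wording needs to change in the Protocol synopsis, Protocol 3.2.2 and 9.4.5, and SAP 2.2.2 and 9.2.1. An analysis of subjects in ICU at baseline could be added as supportive, since that subset is fixed before treatment.

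Also name the source of Day 14 ICU status. The schedule of assessments ticks ICU status only at Day 28 and at Days 60 and 90. The daily procedures in Protocol 8.2.3 list respiratory status and the ordinal scale but not ICU location, and Protocol 8.1.12 covers ICU admissions after the first discharge. The ICU admission and discharge dates needed for the endpoint of ICU days up to Day 90 could serve, if the case report form captures them.

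The cost is a wording change to one secondary endpoint and a check that ICU dates are recorded. The primary analysis and sample size do not change.

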8.1.12. Follow-up contact

The subject will be seen on Day 28 to collect laboratory samples, report on any additional AEs and on the status of unresolved AEs. The subject will also be contacted at Day 60 and 90 to document survival (or collect date of death from family or subject's physician). In addition, any experimental medication, duration of any additional hospital or ICU admissions after the first "post-randomization" discharge will also be collected.

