## **1.0 INTRODUCTION OF THE STATISTICAL ANALYSIS PLAN**

The statistical analysis plan (SAP) is based on protocol STI-5656-2001 ‘A Phase 2, Randomized, Double-Blind, Placebo-Controlled Study of The Safety and Efficacy of Sti-5656 (Abivertinib Maleate) In Subjects Hospitalized Due to Covid-19’, V5.0 dated 07Dec2020. It details the methodology to be used in analyzing the data and outlines the specifications in the Tables, Figures and Listings (TFLs) for data to be included for executing the final statistical analyses for this study.

PK analysis is not included in this plan.

The analyses specified in this document supersede any high-level analysis plan described in the protocol.

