### 7.3 Missing or Incomplete Data

Subjects who are randomized to the study and discontinue before the end of the study will not be replaced. Missing values will not be imputed unless otherwise specified.

For success/failure endpoints, subjects who discontinue prior to the specified time point will be included in the analysis as treatment failures and censored at the last day of follow-up for the time-to-event analysis.

For all other endpoints, the mixed effect model repeat measurement (MMRM) analysis will be employed. The MMRM analysis only includes the available data. It has been demonstrated that the MMRM approach leads to estimators with comparatively small bias, and controls Type I error rates at a nominal level in the presence of missing completely at random (MCAR) or missing at random (MAR) and some possibility of missing not at random (MNAR) data (see <https://pubmed.ncbi.nlm.nih.gov/19212876/>).

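### SAP 9.2.1 applies the discontinuation-as-failure rule to all-cause mortality without an exception; read literally, it counts a subject who leaves the study alive as a death

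*SAP*

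**What the plan says.** SAP 9.2.1 repeats the primary endpoint's method for three groups of secondary endpoints: being alive without respiratory failure at Day 60, being alive and out of the ICU at Days 14 and 28, and "All-cause mortality at Day 60 and Day 90". That method, from SAP 9.1, is a "generalized linear mixed model, assuming a binomial distribution and a logit link" with treatment group as the fixed effect. SAP 6.1 sets the population, which is everyone randomized: "All efficacy endpoints will be analyzed using the FAS".

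The sentence that closes 9.2.1 comes after the whole list: "Subjects who discontinue the study prior to the study day end will be considered treatment failures". It makes no exception for mortality, and neither document says what failure means for that endpoint or that known vital status takes precedence.

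SAP 7.3 has a general rule of the same kind: "For success/failure endpoints, subjects who discontinue prior to the specified time point will be included in the analysis as treatment failures". It also says that missing values are left unimputed unless something else is specified.

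Protocol 9.4.5 (V4.0, the version supplied) is arranged differently. Its failure sentence belongs to the paragraph on ICU discharge and Day 60 freedom from respiratory failure. Mortality comes later, on its own: "The total number of deaths per group will be presented for All-cause mortality at Day 90". That section names no analysis for Day 60 mortality. SAP 1.0 cites protocol V5.0 as its basis and states: "The analyses specified in this document supersede any high-level analysis plan described in the protocol".

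On data collection, Protocol 8.1.12 says: "The subject will also be contacted at Day 60 and 90 to document survival (or collect date of death from family" or from the subject's physician). It does not say whether subjects who have left the study are contacted.

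**The concern.** Treating withdrawal as failure is a usual conservative choice for an endpoint that requires the subject to be alive and in a good state. For mortality, the same rule records an event that is not known to have happened, and it does so even when survival has been documented.

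Two distortions follow. If withdrawal differs between arms, the coded mortality rates differ even when true mortality is equal. If withdrawal is similar in both arms, a true mortality difference is diluted and the odds ratio moves toward 1. Mortality is a named secondary endpoint in a trial of hospitalized COVID-19 patients, and readers will take the reported proportion as a proportion of deaths.

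**Working it through.** **The coding that the text implies.** A binomial model needs a 0/1 outcome for every subject analysed. For mortality the unfavourable state is death. There are four ways to handle a subject who discontinues alive:

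- Code as alive: this makes the subject a success, against the closing sentence of 9.2.1.
- Drop or set to missing: this removes someone whom the sentence counts as a failure and whom the full analysis set includes.
- Rename the outcome as death or discontinuation: the coding is the same, and the endpoint is no longer all-cause mortality.
- Code as dead: this is the coding that follows the sentence as written.

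**Inputs for the illustration.** The 40 per arm comes from SAP 5.0. The documents give neither a mortality rate nor a dropout rate and state no mortality figure to reproduce, so the rates below are assumptions. Let m be true mortality and d the share of survivors who discontinue before the time point.

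**Coded mortality** = m + (1 − m)d. One withdrawn survivor adds 1/40 = 2.5 percentage points.

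| m | d | Coded mortality |
|---|---|---|
| 5% | 5% | 0.05 + 0.95 × 0.05 = 9.75% |
| 10% | 5% | 0.10 + 0.90 × 0.05 = 14.5% |
| 10% | 10% | 0.10 + 0.90 × 0.10 = 19.0% |
| 10% | 15% | 0.10 + 0.90 × 0.15 = 23.5% |
| 15% | 15% | 0.15 + 0.85 × 0.15 = 27.75% |

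**Unequal dropout, equal true mortality of 10%.** The chance of p<0.05 (two-sided) comes from summing exact binomial probabilities over all tables with 40 per arm. For the Wald test from the logit model, tables with no events in an arm count as non-significant.

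| Coded mortality, arm by arm | Pearson | Wald logit |
|---|---|---|
| 10% vs 10% (no dropout) | 5.9% | 1.2% |
| 14.5% vs 19.0% (dropout 5% vs 10%) | 8.6% | 6.2% |
| 14.5% vs 23.5% (dropout 5% vs 15%) | 17.8% | 15.0% |

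The Wald figure of 1.2% is not a fair baseline. The Wald test is very conservative at a 10% event rate with 40 per arm. With no difference between arms it rejects in 3.0% of trials at 14.5%, 4.0% at 19.0% and 4.6% at 23.5%. The 15.0% should therefore be compared with about 3% to 5%.

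**Equal dropout, true mortality 5% vs 15%.** The true odds ratio is (0.05/0.95)/(0.15/0.85) = 0.30.

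| Dropout in both arms | Coded mortality | Odds ratio |
|---|---|---|
| 5% | 9.75% vs 19.25% | 0.45 |
| 10% | 14.5% vs 23.5% | 0.55 |
| 15% | 19.25% vs 27.75% | 0.62 |

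**The case against.** The strongest reply is that the SAP nowhere says that a withdrawn subject is a death. Failure is a natural word for the two composites and an odd one for mortality. Protocol 9.4.5 keeps its failure sentence away from mortality, so the SAP sentence may simply not have been revisited when mortality was added to the list. This stands as a point about intent. It does not rescue the text, because a programmer who follows 9.2.1 has no instruction to treat mortality differently.

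Four stronger readings are tempting, and the documents do not support them:

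- That the sponsor decided to count withdrawals as deaths. This coding is an inference from literal wording, not a stated decision.
- That SAP 7.3 independently imposes the same coding. Its rule covers success/failure endpoints, and neither document classes mortality as one. If mortality falls outside that class, the no-imputation sentence in 7.3 points the other way.
- That the protocol must also be amended. The SAP is based on V5.0, which was not supplied, and it states that it supersedes the protocol's high-level analyses.
- That the rise in Wald rejection from 1.2% to 15.0% is all due to unequal dropout. Part of it comes from the higher event rate.

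There are also partial safeguards. The rule reaches only subjects who leave the study, and the protocol synopsis encourages those who merely stop study drug to remain. Subjects who discontinue because they died are coded correctly. SAP 10.1 tabulates fatal treatment-emergent events separately, and Protocol 8.1.11 collects adverse events through Day 60, so a reader could notice an inflated Day 60 figure. The affected group may be small. These points limit the harm but do not supply a correct mortality analysis.

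**Conclusion.** The point holds as a defect in the SAP's wording: taken literally, 9.2.1 codes a subject who leaves the study alive as a death in the Day 60 and Day 90 mortality analyses. SAP 7.3 has the same effect only if mortality is treated as a success/failure endpoint.

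The size depends on dropout, which the documents do not give. Under the assumed rates, a threefold imbalance in survivor dropout (5% vs 15%) roughly triples the Pearson false-positive rate, from 5.9% to 17.8%. A milder imbalance (5% vs 10%) raises it only to 8.6%. Equal dropout of 10% moves a true odds ratio of 0.30 to 0.55. If nobody leaves the study alive, there is no effect.

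This should be fixed, since it bears on a named mortality endpoint and the correction is cheap. It does not touch the primary analysis, the sample size or the futility rule. The finding lies within the SAP and does not depend on the contrast with protocol V4.0.

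**What to change.** Before unblinding, amend SAP 9.2.1, with a matching clause in 7.3:

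- Exempt all-cause mortality from the discontinuation-as-failure rule, and keep the rule for the two composites.
- Count only documented deaths, using all available vital-status information, including any obtained after discontinuation.
- State how unknown vital status is handled, and do not code it as death. One option is to censor at the date last known alive and give Kaplan-Meier estimates at Day 60 and Day 90; SAP 9.2.4 already plans Kaplan-Meier with censoring for another endpoint.
- Report the number with unknown status in each arm.

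The cost is a few lines of SAP text and a little programming. No protocol change is needed for this, because the SAP supersedes the protocol's analyses. The drawback is that censoring assumes subjects lost to follow-up have the same risk of death as those who are followed, which is why the number unknown per arm must be shown.
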